5.5 Study Evaluations

Consistent with recommendations for determining acceptability and feasibility in the context of intervention development, multiple program aspects will be evaluated with the aim of refining BEAST for larger-scale implementation.^{15–17} Feasibility of BEAST will be indexed via participant retention, average homework completion, and percentage of EMA sessions completed.

Acceptability will be measured using an adaptation of the Program Satisfaction Questionnaire (PSQ), a 14-item measure that assesses both general program satisfaction (usefulness, acceptability) and perceived utility of program components (psychoeducation, EMA/EMI schedule).¹⁸ Measures selected were well-validated, have been administered to Veterans, and/or have been administered via telehealth.

Assessments completed via research staff:

Program Satisfaction Questionnaire (PSQ). Acceptability will be measured using an adaptation of the PSQ, a 14-item measure that assesses both general program satisfaction (usefulness, acceptability) and perceived utility of program components (psychoeducation, EMA/EMI schedule).¹⁸

Blessed Orientation-Memory-Concentration Test (BOMC). The BOMC will be used to screen for cognitive impairment (i.e., ≥ 11).¹⁹

Short Scale Anxiety Sensitivity Index (SSASI).²⁰ The SSASI is a 5-item self-report measure assessing fear of negative consequences of anxiety-related symptoms. Scores ≥ 9 on the SSASI are eligible.

The Anxiety Sensitivity Index-3 (ASI-3).²¹ The ASI-3 is an 18-item self-report measure assessing fear of negative consequences of anxiety-related symptoms.

The Intolerance of Uncertainty Scale-12 (IUS-12).²² The IUS-12 is a 12-item self-report measure assessing fear of uncertainty.

12-Item World Health Organization Disability Assessment Schedule (WHODAS) 2.0. The 12-item version of the WHODAS 2.0 assesses functional impairment across six domains: 1) understanding and communication, 2) self-care, 3) mobility, 4) interpersonal relationships, 5) work and household roles, and 6) community and civic roles.²³

PROMIS Profile-29²⁴. Used to assess the following domains: anxiety, depression, physical function, fatigue, sleep disturbance, ability to participate in social roles and activities, and pain interference.

Functional Impairment Due to COVID (FIDC).²⁵ A 7-item measure adapted from the WHODAS 2.0 to capture difficulties in functioning due to the COVID-19 pandemic, developed and validated by PI [name] and colleagues.

COVID-19 Impact Battery (CIB) Worries.²⁵ An 11-item scale measuring distress and worry due to the COVID-19 pandemic.

COVID-19 Impact Battery (CIB) Behaviors.²⁵ A 12-item scale assessing avoidance behaviors in relation to the COVID-19 pandemic.

Depressive Symptom Index – Suicidality Subscale (DSI-SS). A 4-item measure assessing suicidality within the previous two weeks.

Demographics. At screening, we will assess participants' gender, age, educational background, employment, income, race, ethnicity, marital status, and socioeconomic status.

Exit Interview. The exit interview will assess overall impressions, impact of treatment, relationship with the therapist, and ways to improve the treatment. Acceptability will be measured using an 11-item adaptation of the Program Satisfaction Questionnaire (PSQ) that assesses both general program satisfaction (usefulness, acceptability) and perceived utility of program components (psychoeducation, EMA/EMI schedule).¹⁸ The exit interview and PSQ will inform further refinement of the intervention as needed with our stakeholders. The exit interview will also consist of a number of open ended questions, including prompts to ask for more information, to collect worthwhile feedback on the study procedures, intervention, and their overall feelings toward the intervention.

EMA Measures:

*State Short Scale Anxiety Sensitivity Inventory; SSAS*²⁰: measures anxiety sensitivity.

*State Penn State Worry Questionnaire; PSWQ*⁵¹: measures anxious apprehension.

State Anxiety Depression Distress Inventory-27; ADDI-27: measures anxious arousal

The PSWQ and ADDI-27 have been validated as measures of general anxious apprehension and anxious arousal, respectively, reflecting the two core anxiety dimensions underlying anxiety disorders.^{26,27} Participants will also rate their impairment across functional domains using the

12-item WHODAS 2.0. Visual analog scale (VAS) ratings from 1-100 will be used to assess anxiety, stress, and depression four times daily. ASI-3 items, revised to capture in-the-moment beliefs, will also be completed. Three items will be randomly selected from an ideographically developed pool of items the participant rates as impacting them “much” or “very much.” Thus, the pool of items to be drawn to potentially deliver EMI will differ by individual.

5.6 Schedule of Assessments

Participants will complete virtual baseline, post-intervention, and 1- and 3-month followups. Participants will receive compensation for their participation in the study but not for the intervention session. The compensation amount and sessions attended will be based on the following:

Baseline Assessment	\$40
Face-to-face session	NA
Post-Intervention Assessment	\$40
1-month Assessment	\$30
3-month Assessment	\$30
Weekly EMA Data Collection	\$30 per week
≥ 80% of EMA Weekly Surveys	\$10 per week

Therefore, the total compensation for completing all the study components would be \$340. Payments will be made following each study procedure listed above. Participants who do not complete the entire study for any reason, will receive compensation for the components that were completed per the above schedule of payments.

5.7 Data Analysis

General. To enhance methodological rigor and to allow for accurate dissemination of our findings, we will follow CONSORT guidelines in the design, analysis, and reporting of this study.

Data Management. [name], with the assistance of Drs. [name] and [name], will supervise data management using the following services: Enrollment, randomization, tracking of interviews, and auditing of data. A single enrollment and randomization document will be developed to assign identification codes to participants during the pre-enrollment period to track their eligibility status, and randomly assign participants. Similar to our prior studies, a tracking system will be developed to assist research personnel in managing follow-up interviews. This information will be covered during weekly staffing meetings involving Drs. [name], [name], and [name] as well as the research personnel. Data will be audited for: a) data quality control (% of scales returned for corrections after auditing); b) rate of data entry; and c) backlog of data that has not been entered. All scales will be audited for identifiers, item completeness, and consistency of major clinical indicators. We will store and manage data at the VA with access limited to pertinent study personnel. During the study, we will maintain a dialogue on the technical integrity of our procedures and on conceptual aspects of our project.

Data analysis for Aim 1: Develop expert consensus for our intervention components using a modified Delphi method. Specifically, a modified Delphi Method will facilitate the incorporation of expert and stakeholder feedback to reach consensus.^{38,39} We will present to our stakeholders the results of our study and any proposed changes as-needed after we complete Aim 2 (one-arm trial). Experts and stakeholders will rate each component as: a) acceptable as is, b)

acceptable with minor changes, or c) unacceptable. For each component, our intervention will be considered ready for Aim 2 if at least 4 of 6 clinicians and 4 of 6 veterans meeting eligibility criteria rate it to be acceptable as is and two rate it as acceptable with changes. If any member rates the content as unacceptable, we will meet with these participants individually to discuss why they rated the intervention as such. Experts and stakeholders will again evaluate any component of the intervention that did not meet eligibility criteria after the initial round of review. determine if the change would invalidate the intervention. If so, the team will agree not to make the suggested change. Correspondence with the expert panel will be done via email and virtual meetings. A final meeting regarding the summarized findings from the second round of feedback will be held by the investigative team to finalize the protocol. We will meet with our stakeholders to resolve any disagreements between the investigative team and our stakeholders.

Data analysis for Aim 2: Assess the feasibility, acceptability, and usability of BEAST. We will track the number of Veterans who are recruited per month. We will calculate the percentage of participants who complete the protocol and follow-ups to calculate acceptability. Treatment acceptability will be assessed with the exit interview. Therapist fidelity scores for the individual session will be assessed as the percentage of the content delivered. Interrater reliability for fidelity and competence will be assessed using intraclass correlation coefficients. When incorporating information from the exit interview, raters will provide perspectives, discuss their summarized responses, and reach consensus on different factors (e.g., format, receptivity, feasibility).

The PI will check the work of the raters and chart the data to further examine the domains, core ideas, and categories that describe the themes. Means and standard deviations for outcomes will be calculated at each assessment, including change scores and correlations across timepoints. We expect large standard errors due to sample size. Distribution of scores will be examined to better evaluate how to analyze these data in future studies. For continuous outcomes, Hedge's g will be calculated to identify a range of the pre-post effect size. Although such calculations are of limited benefit in determining the effect of the intervention, they are helpful in identifying outcomes for which the intervention may be less effective.

For data quality and handling of missing data, descriptive statistics will help identify out of range values and outliers. *The assessment battery* will be considered acceptable if no questionnaires are missing in full in more than 25% of the participants and if reliability is higher than 0.70. *Acceptability of EMA procedures* will be assessed through calculating the percentage of EMA surveys completed as well as completion patterns. BEAST will also be considered feasible and acceptable if $\geq 70\%$ of the EMA sessions are completed by $\geq 80\%$ of participants, consistent with prior rates in studies conducted and reviewed by [name]. Acceptability will also be measured using an adaptation of the PSQ, an 11-item measure that assesses both general program satisfaction (usefulness, acceptability) and perceived utility of program components (face-to-face sessions, EMA/EMI).¹⁸ Finally, an average PSQ general satisfaction score of ≥ 4 (on a 5-point scale) and an average PSQ mobile app score ≥ 4 (on a 5-point scale) will provide support for the feasibility and acceptability of BEAST. The research team and stakeholders will

meet and discuss the intervention regarding benchmarks of acceptability and feasibility as well as the information gathered during the exit interviews.

Power analysis. As this is a pilot trial, we did not conduct a formal power analysis when selecting the sample size. Rather, we used stepped rules of thumb to optimize the overall sample size for the pilot and main effects study.²⁸ Based on these stepped rules of thumb and an expectation of clinical effect sizes in the medium range on primary and secondary outcomes of the RCT, 15 participants is considered adequate.

Future trial. Findings from this pilot trial will provide the necessary infrastructure and demonstration of feasibility to allow us to expeditiously conduct a fully powered RCT and then disseminate through the VA. At the completion of this study, we will have refined the treatment manual, the mobile app design and schedule, and the study protocol/pipeline. Therefore, it is expected we will be well-positioned to pursue a MERIT award to provide evidence of efficacy of BEAST.

Data storage, security, and confidentiality. Several procedures for protecting participant confidentiality will be implemented to reduce the risk of revealing participant identity. All informed consent forms will contain identifying information. To ensure confidentiality, each consent form will be labeled with a numeric identifier and will be stored in a double-locked file. These will be stored in separate double-locked files from other study materials.

The VA Informatics and Computing Infrastructure (VINCI) will be used for the storage of study data. VINCI is a major informatics initiative of the Department of Veterans Affairs (VA) that provides a secure, central analytic platform for performing research and supporting clinical operations activities. It is a partnership between the VA Office of Information Technology (OI&T) and the Veterans Health Administration Office of Research and Development (VHA ORD). VINCI includes a cluster of servers for securely hosting suites of databases integrated from select national VA data sources. VINCI servers for data, applications, and virtual sessions are physically located at the VA Austin Information Technology Center (AITC), located in Austin, Texas. This secure enclave with 105 high-performance servers and 1.5 petabytes of high-speed data storage has multiple layers of security and disaster recovery to prevent data loss.

Study data will be kept in accordance with the Department of Veterans Affairs Record Control Schedule 10-1 (RCS 10-1). Storage and transfer of any Personally Identifiable Information (PII) or Protected Health Information (PHI) must be done in accordance with applicable VA and VHA policies and directives, state and federal regulations, and applicable statutes including the Health Insurance Portability and Accountability ACT (HIPAA). Unless explicitly requested and approved by data stewards, all sensitive patient data must remain on VINCI project servers and only aggregate data without PII / PHI may be transferred from VINCI. At the completion of the study, disposition of records will also follow guidelines of RCS 10-1 in accordance with VA, VHA, and HIPAA policies and directives as mentioned previously.

Prior to being uploaded to VINCI for analysis, data will be stored on a secure VA server, which is password protected, and to which only IRB approved VA research personnel have access. Should any identifiable information need to be shared between research sites, research teams

will utilize a secure, SharePoint site or electronic communication with PKI encryption. Any identifiable paper data will be stored in two separate locked file cabinets (one for informed consents and the other for paper questionnaire data) in the offices of the Center for Excellence for Suicide Prevention at the Canandaigua VAMC and VA Center for Integrated Healthcare at the Buffalo VAMC. After a participant completes the study, any identifiers will be removed from the paper questionnaire data immediately. Data analysis will occur in the VINCI framework.

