5.0 Study Procedures

5.1 Study Design

Aim 1 Study Design

Study sample and Screening: We will recruit 6 therapists with experience in telehealth and CBT treatment of Veterans with anxiety and 6 Veterans who meet study eligibility for Aim 2 through the Canandaigua, NY VA.

Assessments and Intervention: Stakeholders (masters-level or higher therapists and Veterans meeting eligibility criteria) will be enrolled following consent. Separate consent forms have been developed for the initial session and the second session. The framework for BEAST exists and will be refined based on feedback received from stakeholders. BEAST comprises two components: face-to-face virtual sessions delivered via telehealth and EMI based on the skills acquired in session, delivered via mobile app. Stakeholders will be asked a series of open- and close-ended questions about the intervention (see Appendix) using an evidence-based expert consensus method for refining the intervention and tailoring the protocol for Veterans. Stakeholders will evaluate the final product after we have completed the one-arm trial and compiled and organized the exit interview information. Final modifications will be incorporated again through seeking consensus with stakeholders.

The study team will work with the Center for Mobile Applications Research Resources & Services (CMARRS) to refine the mobile app and therapist dashboard that will be used to deliver the EMA/EMI components of the intervention. The initial development will occur with the study team using the Mobile App Rating Scale, a multi-dimensional scale assessing an app's engagement, functionality, aesthetics, information, and subjective quality as well as items assessing the perceived impact of the app on the target audience's knowledge, attitudes, intentions to change and likelihood of changing.⁴⁰ Ratings across scales range from 1 ("inadequate") to 5 ("excellent"). We will proceed with our app once it receives consensus scores of 4 or higher across all scales among the study team. In the unlikely event that consensus ratings are not achieved, we will resolve through a study team meeting and a simple majority being used to select consensus.

Veteran participants will receive compensation for their participation in the study. The compensation amount will be based on the following:

Prior to Pilot Study	\$50
Completion of Pilot Study	\$50

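### The Aim 1 stakeholder readiness rule, read literally, fails a component that every rater accepts as is, and does not say whether an unacceptable rating blocks readiness

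*Combined protocol and SAP*

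**What the plan says.** Section 5.1 (Aim 1 Study Design) sets up two panels: "We will recruit 6 therapists with experience in telehealth and CBT treatment of Veterans with anxiety and 6 Veterans". In section 5.7 (data analysis for Aim 1) each rater gives a component one of three ratings. The first accepts it unchanged; the other two are "acceptable with minor changes, or c) unacceptable". A component is "ready for Aim 2 if at least 4 of 6 clinicians and 4 of 6 veterans meeting eligibility criteria" choose the as-is rating. The same sentence attaches the with-changes condition: "rate it to be acceptable as is and two rate it as acceptable with changes".

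Two provisions follow. On rejection: "If any member rates the content as unacceptable, we will meet with these participants individually to discuss why they rated the intervention as such". On missing the rule: "Experts and stakeholders will again evaluate any component of the intervention that did not meet eligibility criteria after the initial round". Section 5.7 also provides for a final investigator meeting on the second-round findings and for a meeting with stakeholders to settle remaining disagreements.

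**The concern.** The with-changes condition is joined to the as-is condition by *and*, so on its face it must be met. Nothing says whether the two raters are counted per panel or in total, or whether the number is exact, a minimum or a maximum. No other section settles this.

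A threshold fixed in advance should not reject the best possible result. It should also say what a rejection does. Here the sentence on unacceptable ratings prescribes a conversation and is silent on readiness. The re-rating sentence gives no separate protection, because it applies only to components that miss the ambiguous rule. Two team members applying the text in good faith to the same 12 ratings could reach different conclusions about whether a component is ready for the 15 Aim 2 Veterans.

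**Working it through.** **Inputs.** Six clinicians and six Veterans (section 5.1). Three mutually exclusive ratings, and the thresholds of 4, 4 and 2 (section 5.7). The plan gives no calculation for this rule, so there is no stated figure to reproduce; the check is a full count of possible ratings.

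**Notation.** Write one panel's ratings as (as-is, with-changes, unacceptable) = (a, b, c), with a + b + c = 6. There are 8 × 7 / 2 = 28 such splits per panel and 28 × 28 = 784 joint splits for the two panels.

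**Splits with a ≥ 4.** There are six: (4,2,0), (4,1,1), (4,0,2), (5,1,0), (5,0,1), (6,0,0). By number of with-changes ratings: one has b = 2, two have b = 1, three have b = 0.

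**Reading 1: two per panel.** This requires a ≥ 4 and b = 2 (or b ≥ 2). Since 4 + 2 = 6, only (4,2,0) passes.
- 1 of 28 splits per panel and 1 of 784 joint splits.
- (5,1,0) and (6,0,0) fail, so the words allowing more than four as-is ratings have no effect.
- No unacceptable rating can pass.

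**Reading 2: two across both panels.** This requires a ≥ 4 in each panel and a with-changes total of two.
- Exactly two: (1 × 3) + (2 × 2) + (3 × 1) = 10 joint splits pass.
- At least two: add totals of three, (1 × 2) + (2 × 1) = 4, and of four, 1 × 1 = 1, giving 15.
- All 12 as-is has a with-changes total of 0 and fails in both cases.
- Raters accounted for: 4 + 4 + 2 = 10, leaving 12 − 10 = 2. Both may rate unacceptable and the component still passes, for example clinicians (4,0,2) with Veterans (4,2,0).

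**Probable intent: a ≥ 4 and c = 0 in each panel.** Three splits per panel pass, (4,2,0), (5,1,0) and (6,0,0), so 3 × 3 = 9 joint splits.

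| Reading | Joint splits that pass | All 12 as-is | Most unacceptable ratings in a passing split |
|---|---|---|---|
| Two per panel | 1 | fails | 0 |
| Exactly two in total | 10 | fails | 2 |
| At least two in total | 15 | fails | 2 |
| Probable intent (not written) | 9 | passes | 0 |

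**Would inserting *up to* before *two* be enough?** No. With a ≥ 4, b can never exceed 2 in a panel, so a per-panel cap adds nothing. All six splits listed above would pass, including (4,0,2) in each panel, which is 2 + 2 = 4 rejections.

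**The case against.** The strongest reply is that the intent is plain. Four plus two makes six, so the authors surely meant that the raters who do not choose as-is should be no worse than with-changes. A team is unlikely to fail a unanimously approved component. This is probably right about intent, and it disposes of the unanimous case in practice. It does not supply the missing statement about unacceptable ratings, which the plan treats as grounds for a conversation and nothing more.

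Several stronger readings are tempting, but the documents do not support them.
- A reader might infer that this rule alone controls entry to Aim 2. Section 5.1 has a separate criterion for the app (study-team consensus scores of 4 or higher, with a majority fallback), and section 5.7 adds the second round and the closing meetings.
- A reader might infer that the rule decides whether the pilot goes ahead. It works component by component, and a miss leads to re-rating.
- A reader might take it as certain both that one unanimous panel fails and that rejected content can pass. The first holds only on the per-panel count, since (6,0,0) with (4,2,0) passes when panels are pooled. The second holds only on the pooled count. Failure of all 12 as-is is common to both.
- A reader might say that two raters are wholly unconstrained. That needs at least two with-changes ratings in total. If the number is exact, the remaining two may choose as-is or unacceptable but not with-changes. Two rejections are possible either way.
- A reader might treat 1 of 28 as a probability. It is a count of possible splits, which are not equally likely.
- A reader might count the incomplete sentence after the re-rating provision as a further defect. Text lost in conversion cannot be excluded, and nothing here depends on it.

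**Conclusion.** The rule is wrong as written and should be reworded. Under each literal count it fails unanimous as-is approval by all 12 raters. Counted per panel, it passes only (4,2,0) in both panels. Counted across panels, it lets through a component that up to 2 of 12 raters call unacceptable, because the prescribed meeting is not said to block readiness.

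This rests on taking *and two* as a requirement, on each rater giving one rating per component, and on both panels being complete at six.

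The consequence is small. The likely costs are an unnecessary second round for a well-received component, or a dispute about whether an objection counts. Aim 2 estimates and benchmarks do not depend on the rule.

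**What to change.** Restate the rule in section 5.7 along these lines: *A component is ready for Aim 2 if at least 4 of 6 clinicians and at least 4 of 6 Veterans rate it acceptable as is, and the remaining raters in each panel (up to two) rate it acceptable with minor changes.* Then add: *A component with any unacceptable rating in the first round goes to the individual meeting and to second-round rating; any disagreement that remains is resolved at the final investigator meeting and the stakeholder meeting.*

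This passes the 5-1 and 6-0 splits, states what a rejection does, and uses only steps the plan already contains. The cost is two sentences, with no change to sample size or Aim 2 assessments. The downside is that one rater can send a component to the second round. Because remaining disagreements go to the planned meetings, that rater does not hold an indefinite veto. If the investigators prefer that a single objection should not trigger re-rating, that is their choice, but the rule should then state how many unacceptable ratings are tolerated in each panel.

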Assessments and Intervention: Veterans will be enrolled following informed consent. Veterans will next complete the baseline assessment. At the baseline assessment, Veterans meet with the Project Coordinator by phone or virtually to complete a consenting process, guidance on the video software being used, and set-up and guidance of the mobile app. Research team member will reach out to the Veteran the following day to address any issues with using the app. Veteran will complete assessment surveys for approximately 1 week. At the baseline appointment, participants will be scheduled to receive the face-to-face virtual intervention followed by two weeks of EMA/EMI via mPRO. At the end of the two weeks, Veterans will complete a post-intervention assessment appointment. Follow-up assessment appointments will be completed at the 1-month and 3-month follow-ups. The post-intervention assessment includes an exit interview for participants to provide additional feedback regarding acceptability of the intervention. The research staff will read the measures to the Veteran who will verbally provide their answers; we have found this improves data reliability and completeness immensely compared to mailing packets/sending survey links.

BEAST contains two components: First, there is a single session **face-to-face virtual intervention** delivered by the counselor or therapist, delivered via VA Video Connect software. Second, a **mobile app (mPRO) is used for EMA and to deliver EMI components.**

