Face-to-face session. The face-to-face session is a one-hour manualized intervention that uses interactive content to enhance participant learning of critical intervention components. The session includes 1) psychoeducation regarding the role of anxiety sensitivity in exacerbating anxiety sensations, 2) practice identifying and challenging maladaptive thoughts about anxiety, and 3) an IE activity. Psychoeducation is first provided, focusing on the body's alarm system with a goal of normalizing bodily sensations associated with anxiety. Following psychoeducation, the participant and therapist discuss sensations the participant experiences when they are anxious and the thoughts about these sensations that serve to maintain them. The participant and therapist explore challenges to any strongly held beliefs about the danger of anxiety sensations. Finally, the IE consists of: repeated trials of hyperventilation given evidence that this challenge is among the most anxiety-provoking for individuals with panic disorder and our experience using this IE exercise in prior RCTs,¹⁰⁻¹² as well as repeated trials of another selected interoceptive exposure activity. To aid in personalization, Veterans assist in choosing 3 **key takeaways** that summarize what they learned from the intervention regarding anxiety sensations as benign. Common summaries from past participants include: *Anxiety sucks, but it is harmless; I've been anxious before, no big deal!* These summary phrases are incorporated into the EMI. Participants are also asked to complete one set of IE exercises daily for the next two weeks.

EMA. EMA will be collected from baseline to post-intervention and for one week after completing each follow-up. This measurement burst design allows for ratings of functional impairment and anxiety to be calculated disambiguated from state level influences. In our future RCT, this will provide additional power to explore the mechanisms at play. Consistent with best-practice recommendations¹³ we will employ a mixture of *fixed time-based sampling*, *experience sampling*, and *event-based sampling* strategies. In the morning, participants will receive a fixed time-based survey that will include a short battery of questions that will take approximately 2

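### Does the EMA completion benchmark need a rule for follow-up bursts that are never sent?

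*Combined protocol and SAP*

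**What the plan says.** The benchmark is in section 5.7 (Data Analysis, Aim 2): "BEAST will also be considered feasible and acceptable if" at least 70% of EMA sessions are completed by at least 80% of participants. The same section assesses EMA acceptability by "calculating the percentage of EMA surveys completed as well as completion patterns". It also reports the percentage of participants who finish the protocol and the follow-ups, and it sets a separate tolerance for the questionnaire battery: "no questionnaires are missing in full in more than 25% of the participants".

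The EMA schedule is in section 5.1. Overall, "EMA will be collected from baseline to post-intervention and for one week after completing each follow-up". The baseline part is given as "Veteran will complete assessment surveys for approximately 1 week", and the session is "followed by two weeks of EMA/EMI via mPRO". Each day has one morning survey and three quasi-random ones. There are two follow-ups, at 1 and 3 months.

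Section 5.6 pays $30 per EMA week plus $10 for "≥ 80% of EMA Weekly Surveys", with a total of $340.

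Section 5.5 names the feasibility indices: "Feasibility of BEAST will be indexed via participant retention, average homework completion, and percentage of EMA sessions completed".

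**The concern.** The benchmark sentence names neither its window nor its denominator. Because a follow-up EMA week comes after the follow-up visit, a Veteran who misses the visit may never be sent that week's surveys. They could then be scored as missed, or as not due.

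The two scorings measure different things. If unsent surveys count as missed, the EMA mark becomes partly a retention mark. If they are left out, a Veteran who leaves early can meet the mark on very few surveys. Feasibility is the purpose of Aim 2, so a benchmark that could read as met or not met from the same data deserves a look.

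Two smaller points came with it. Average homework completion is an index in section 5.5 but is not repeated in section 5.7. Retention is filed under feasibility in section 5.5 and under acceptability in section 5.7.

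**Working it through.** **Number of EMA weeks, from the plan's own total.** The four assessments in section 5.6 pay 40 + 40 + 30 + 30 = $140. Each EMA week pays up to 30 + 10 = $40. So (340 − 140) / 40 = 5 weeks. This agrees with section 5.1: 1 baseline + 2 EMA/EMI + 1 + 1 follow-up. The plan's figure reproduces, and only five weeks gives $340.

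**Surveys and thresholds.** 4 per day × 7 = 28 per week, and 28 × 5 = 140 in all, taking the baseline week as exactly 7 days. The 70% bar is 0.70 × 140 = 98 surveys. The 80% bar is 0.80 × 15 = 12 Veterans.

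**One Veteran who misses one follow-up** (assuming that burst is not sent). The weekly payment level is 0.80 × 28 = 22.4, so 23 surveys. Over four weeks sent, 4 × 23 = 92.

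- Unsent week left out: 92 / 112 = 82.1%, meets 70%.
- Unsent week counted: 92 / 140 = 65.7%, does not.

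The scorings part for any completion rate from 70% up to just under 98 / 112 = 87.5% of the surveys sent.

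**A Veteran who leaves early.** Someone who withdraws after the baseline week with 20 / 28 = 71.4% meets the bar if unsent surveys are left out. Someone who answers everything to post-intervention and then attends no follow-up scores 84 / 84 = 100% or 84 / 140 = 60%.

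**A pilot built to flip.** Three Veterans at 23 of 28 each miss one follow-up, one other answers under 70%, and the remaining 11 meet the bar. Left out: 14 / 15 = 93.3%, benchmark met. Counted: 11 / 15 = 73.3%, not met.

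**How often that might happen.** The documents give no attendance or completion rates, so these are assumptions: personal completion Beta-distributed with mean 75%, 80%, 85% or 90% and SD 10 or 15 points, the same in every week sent; each follow-up attended independently of the other and of completion; 200,000 simulated pilots of 15 per setting.

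| Attendance per follow-up | Scorings disagree: range over 8 settings | Median |
|---|---|---|
| 90% | 6% to 41% | 22% |
| 95% | 2% to 21% | 9% |

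The 41% arises at mean 80%, SD 10 points. In every disagreement, leaving unsent surveys out meets the mark and counting them does not.

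**Precision of the mark itself.** Exact 95% intervals: 12/15 gives 52% to 96%; 11/15 gives 45% to 92%. The results on either side of the threshold are barely distinguishable.

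**The case for a change.** The best case for a change is that the arithmetic is sound and the cure is one sentence. Follow-up weeks are 2 of 5, or 56 of 140 surveys (40%), so their scoring is not a detail at the margin. Describing completion patterns does not define a pass mark, and the team will cite demonstrated feasibility when it proposes the larger trial.

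Part of this stands. The scoring of unsent bursts is not written down, and a report that gives the benchmark result should name the denominator used.

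The rest weakens on inspection. Section 5.1 fixes the timing of each burst but does not say that it is withheld when a visit is missed, so the mechanism is partly assumed. The disagreement rates come wholly from assumed inputs, and the 14/15 versus 11/15 pilot was chosen to straddle the line: it shows that a flip is possible, not that it is likely. Either scoring is defensible once named, so no stated rule produces a wrong answer.

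The smaller points do not add weight. Section 5.5 already names average homework completion as an index. Section 5.1 sets it at one set of interoceptive exercises daily for two weeks, tracked by event-based sampling. No pass mark is promised for it. Section 5.7 treats feasibility and acceptability together and calculates retention whichever label it carries.

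**Conclusion.** No change to the plan is needed. This is a gap in detail that an analyst would fill sensibly: the schedule and the $340 total define five EMA weeks, 15 Veterans are enrolled, and the plain reading of the benchmark is all scheduled surveys for all of them, with unsent surveys not completed.

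For a single Veteran the choice can move the score from 66% to 82%. For the pilot it could move the benchmark from not met to met, with a frequency that ranges from 2% to 41% under assumptions the documents neither support nor rule out.

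Little rests on the outcome. The benchmark sits beside satisfaction scores and the battery criterion, the reported completion patterns and follow-up completion would show where surveys are missing, and the team and stakeholders then discuss the results together. The conclusion assumes 7-day EMA weeks, four surveys a day, and that a missed follow-up visit means no burst.
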